Official Title : Efficacy of Light Therapy in Improving Sleep Quality, Fatigue, and Emotional Symptoms in Patients with Gynecologic Cancer

NCT 編號 : Pending

Document Date : 2024.12.15

Efficacy of Light Therapy in Improving Sleep Quality, Fatigue, and Emotional Symptoms in Patients with Gynecologic Cancer

Abstract

Objective: This study aims to examine the efficacy of light therapy in improving sleep quality, reducing fatigue, and alleviating emotional symptoms among patients diagnosed with gynecologic cancer.

Methods: A randomized controlled trial was conducted at a medical center in northern Taiwan. Participants were eligible if they were aged 18 years or older, had a physician-confirmed diagnosis of gynecologic cancer, and reported an Insomnia Severity Index – Chinese version (ISI-C) score of ≥ 9 . Eligible participants were randomly assigned to either an experimental group or a control group ($n = 47$ per group). At baseline (T0), participants completed a demographic questionnaire, ISI-C, the Brief Fatigue Inventory – Taiwanese version (BFI-T), and the Distress Thermometer (DT). The experimental group received daily morning light therapy for 30–40 minutes over four weeks using a circadian-regulating light device. The control group continued their usual routines during the same period. Follow-up assessments were scheduled at day 7 (T1), day 14 (T2), day 21 (T3), and day 28 (T4). Data will be analyzed using generalized estimating equations (GEE) to evaluate the effects of the intervention on sleep quality, fatigue, and emotional symptoms.

Keywords: light therapy, gynecologic cancer, chemotherapy, sleep quality, fatigue, emotional symptoms.

Research Motivation and Significance

Gynecologic malignancies, including cervical, endometrial, and ovarian cancers, account for approximately 14.4% of all female cancers in Taiwan. Chemotherapy remains a mainstay treatment but is often accompanied by adverse symptoms such as fatigue, emotional distress, and sleep disturbances—each significantly impairing quality of life and possibly prognosis. Approximately 9% to 45% of cancer patients experience moderate-to-severe fatigue, and over half of women with gynecologic cancer report persistent sleep disturbances, often worsened by psychological symptoms. While pharmacological treatments exist, they frequently cause undesirable side effects. Consequently, interest has grown in non-pharmacological interventions like light therapy, which modulates circadian rhythms through suppression of melatonin and enhancement of serotonin. Re-Timer® light therapy glasses (500 nm wavelength, 500 lux) offer a safe, user-friendly, FDA-cleared home-based solution. By stimulating intrinsically photosensitive retinal ganglion cells (ipRGCs) and acting on the suprachiasmatic nucleus (SCN), Re-Timer® stabilizes circadian rhythms, thereby potentially improving sleep, fatigue, and mood regulation. Despite growing evidence, limited studies have evaluated the efficacy of light therapy in gynecologic cancer survivors. This study aims to assess the therapeutic effects of bright light therapy using Re-Timer® in alleviating chemotherapy-related sleep disturbances, fatigue, and emotional distress, and to provide evidence for clinical implementation of non-pharmacological symptom management strategies in this population. Methods

Research Design

This study utilized a randomized controlled trial (RCT) design and was implemented at the gynecologic outpatient department of a tertiary medical center in northern Taiwan.

Research Setting and Participants

This study was conducted at a tertiary medical center in northern Taiwan between May 13 and December 12, 2024. Eligible participants were individuals aged 18 years or older with a physician-confirmed diagnosis of gynecologic cancer and an Insomnia Severity Index-Chinese version (ISI-C) score of 9 or above. All participants provided written informed consent prior to enrollment. Exclusion criteria included the presence of visual impairment or photosensitivity that could interfere with the use of light therapy devices, a current diagnosis of psychiatric disorders or cognitive impairment, and any physical limitations that would hinder adherence to the intervention protocol or data collection due to disease severity.

Sample Size Calculation and Randomization

Sample size was calculated using G*Power 3.1, assuming a medium effect size ($f = 0.25$), a significance level of $\alpha = 0.05$, and a statistical power of 0.80 for a two-group comparison. The estimated minimum sample size was 78 participants. Allowing for an anticipated attrition rate of 20%, the target enrollment was increased to 94 participants. Participants were randomly assigned to either the experimental or control group in a 1:1 ratio using the random number generator function in Microsoft Excel (Microsoft Corporation, Redmond, WA, USA). Each group ultimately included 47 participants.

Data Collection and Ethical Considerations

Ethical Approval and Informed Consent : The study protocol was approved by the Institutional Review Board (IRB) of the participating medical center (CGH-IRB No. 202400345A3C601). Participant recruitment was conducted in the gynecologic outpatient department. Before enrollment, all participants received a thorough explanation of the study's objectives, procedures, potential risks, and anticipated benefits. They were assured that their personal data would be anonymized, securely stored, and used solely for academic research purposes. Participants were informed of their right to withdraw from the study at any time without affecting their ongoing clinical care. Written informed consent was obtained from all participants.

Baseline Assessment and Intervention : Following consent, participants completed baseline assessments (T0), including a demographic and treatment questionnaire, the Insomnia Severity Index – Chinese version (ISI-C), the Taiwanese version of the Brief Fatigue Inventory (BFI-T), and the Distress Thermometer (DT). Participants randomized to the experimental group were instructed to wear the Re-Timer® circadian regulator glasses for 30–40 minutes each morning within 30 minutes of waking, for four consecutive weeks. Participants recorded daily light therapy duration and sleep hours. If any discomfort occurred during the intervention, therapy was discontinued immediately, and support was provided by the research team. The control group was instructed to continue their regular daily routines without any light therapy intervention.

Follow-up Assessments : Outcome measures (ISI-C, BFI-T, and DT) were reassessed via an online questionnaire delivered through the LINE messaging app on Days 7 (T1), 14 (T2), 21 (T3), and 28 (T4) after the start of the intervention

Measurement Instruments

Demographic and Treatment-Related Variables :

Data collected included participants' age, body mass index (BMI), education level, marital status, religious affiliation, employment status, cancer type, cancer stage, use of sleep medications, and history of emotional distress. Treatment-related variables encompassed the current treatment modality, time since treatment completion, and general health status.

Sleep Quality :

Sleep quality was assessed using the Chinese version of the Insomnia Severity Index (ISI-C), which evaluates the severity and impact of insomnia symptoms over the past two weeks. The seven items cover:

Difficulty initiating sleep

Difficulty maintaining sleep

Early morning awakening

Satisfaction with current sleep pattern

Interference with daily functioning

Noticeable impairment in quality of life due to sleep problems

Degree of worry or distress about sleep difficulties

Each item is rated on a 5-point Likert scale (0–4), with total scores ranging from 0 to 28; higher scores indicate more severe insomnia. The original ISI was developed by Morin et al. (1993), and the Chinese version was validated by Yang et al. (2009). The ISI-C demonstrates excellent internal consistency (Cronbach's $\alpha = 0.91$) and high concurrent validity with the Chinese version of the Pittsburgh Sleep Quality Index ($r = 0.88$). A cutoff score of ≥ 9 yields a sensitivity of 91.8% and specificity of 91.2%.

Fatigue :

Fatigue severity was measured using the Taiwanese version of the Brief Fatigue Inventory (BFI-T), which was originally developed at the University of Texas MD Anderson Cancer Center (Mendoza et al., 1999). The BFI-T assesses fatigue experienced in the past 24 hours across nine items, each rated from 0 (no fatigue) to 10 (worst imaginable fatigue). The total score ranges from 0 to 90, with higher scores indicating greater fatigue severity. The BFI-T has demonstrated excellent reliability, with a Cronbach's α of 0.97 and test-retest reliability of 0.91 (Lin et al., 2006).

Emotional Symptoms :

Emotional distress was assessed using the Distress Thermometer (DT), a validated visual analog scale developed by Roth et al. (1988) to screen for distress caused by illness-related emotional issues such as anxiety, sadness, fear, and depression. Participants rate their level of distress on a scale from 0 (no distress) to 10 (extreme

distress), with a score of 5 representing moderate distress. In clinical practice, a cutoff score of 4 is commonly used to indicate significant distress. The Chinese version of the DT was adapted from the version provided by the National Comprehensive Cancer Network (NCCN). Wang et al. (2011) reported a sensitivity of 98% and a specificity of 73% for the DT.

.Statistical Analysis

All statistical analyses were performed using IBM SPSS Statistics version 26.0. To evaluate baseline homogeneity between the experimental and control groups, independent samples t-tests were used for continuous variables, while chi-square (χ^2) tests or Fisher's exact tests were applied for categorical variables, as appropriate. The effectiveness of the light therapy intervention on sleep quality, fatigue, and emotional distress across time points was assessed using generalized estimating equations (GEE), which account for correlated repeated measures and accommodate missing data. Statistical significance was set at a two-tailed p value of < 0.05 .

Results

A total of 94 participants diagnosed with gynecologic cancer were enrolled and randomly allocated into the experimental and control groups with a 1:1 ratio (47 per group). During the study period, four participants withdrew due to health-related reasons, resulting in a final sample size of 90 (44 in the experimental group and 46 in the control group). The mean age was approximately 52 years. Baseline demographic and clinical characteristics were analyzed to ensure group equivalence. All variables were comparable between groups, except for body mass index (BMI), which showed a statistically significant difference and was adjusted for in subsequent analyses.

Primary and Secondary Outcomes :

Participants completed outcome assessments at baseline and weekly intervals for four weeks following the intervention (T1–T4). Sleep quality was assessed using the

Insomnia Severity Index – Chinese version (ISI-C).Fatigue was evaluated using the Brief Fatigue Inventory – Taiwan version (BFI-T).Emotional distress was measured using the Distress Thermometer (DT).All instruments were administered at baseline (T0), and at days 7 (T1), 14 (T2), 21 (T3), and 28 (T4).

Changes in these outcomes across timepoints and between groups were analyzed using generalized estimating equations (GEE), with BMI included as a covariate to adjust for baseline differences. This model allowed for evaluation of group, time, and interaction effects on outcome measures.

References

Çelik, A., & Usta Yeşilbalkan, Ö. (2023). The Effect of the Bright White Light Application to Cancer Patients Receiving Palliative Care on Their Fatigue Level and Sleep Quality: A Randomized Control Trial. *Omega*, 88(1), 303–317. <https://doi-org.libermg.cgmh.org.tw:8443/10.1177/00302228221093462>

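### The 0.80 power stated for 78 participants does not follow from the stated inputs, which alone need 128; the settings that would give 78 are not reported, so the effect that was powered is unknown

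*Combined protocol and SAP*

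**What the plan says.** Methods, Sample Size Calculation and Randomization: "Sample size was calculated using G*Power 3.1, assuming a medium effect size" of f = 0.25 with α = 0.05, then "a statistical power of 0.80 for a two-group comparison. The estimated minimum sample size was 78 participants". Enrolment was raised to 94 for attrition. The section names no G*Power test, number of measurements, within-person correlation, outcome or time point, and no correlation between visits appears anywhere in the document.

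The design has five assessments. T0 is completed before the intervention starts, and T1 to T4 follow at days 7, 14, 21 and 28.

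Statistical Analysis sets a two-tailed 0.05 level and analyses the outcomes by GEE. Results, Primary and Secondary Outcomes, says of that GEE: "This model allowed for evaluation of group, time, and interaction effects on outcome measures". The only covariate named is BMI ("with BMI included as a covariate to adjust for baseline differences"). Neither section says which of the three effects the sample size was meant to support. Results also reports four withdrawals, "resulting in a final sample size of 90 (44 in the experimental group and 46 in the control group").

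**The concern.** The power statement looks complete: software, effect size, level, power, number of groups and answer. A reader who enters those values into a two-group calculation gets 128, not 78. Either an unstated design feature was used or the figure is wrong, and the text does not allow the two to be told apart.

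What is at stake is interpretation. Enrolment is finished, so nothing about conduct changes. If a result is non-significant, however, a reader may take it that a medium treatment effect had 80% power. Whether that is so depends on which effect the 0.80 was attached to, and the most plausible source is not the group-by-time effect that describes how the arms diverge after T0.

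**Working it through.** **Inputs.** From the sample-size section: f = 0.25 (for two equal groups d = 2f = 0.5), α = 0.05, power 0.80, two groups, 1:1 allocation. From Statistical Analysis: two-tailed testing. From the visit schedule: five occasions, of which four follow the start of treatment. Assumed because not stated: correlation ρ, exchangeable, shown at 0.3, 0.5 and 0.7. N is the smallest even total reaching 0.80, from the noncentral F distribution.

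**1. Stated inputs alone.** λ = f²N, df 1 and N − 2.
- N = 126: power 0.7952. N = 128: λ = 0.0625 × 128 = 8.0, power 0.8015. So 128 are needed.
- N = 78: λ = 0.0625 × 78 = 4.875, power 0.5871.
- N = 90: power 0.6502. N = 94: power 0.6695.

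The stated 78 is not reproduced.

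**2. Adding repeated measures, between-groups test.** λ = f²N·m/(1 + (m − 1)ρ), df 1 and N − 2, where m is the number of occasions.
- m = 5, ρ = 0.5: N = 76 gives 0.7930; N = 78 gives λ = 0.0625 × 78 × 5/3 = 8.125, power 0.8035. So N = 78.
- m = 4 at ρ of about 0.46, m = 3 at ρ = 0.4, and m = 2 at ρ = 0.2 also return 78.
- m = 4 at ρ = 0.5 does not: 78 gives 0.7874 and 82 are needed.

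Five occasions at 0.5 fits the T0–T4 schedule and uses a round correlation, so it is the most plausible source, but it is not the only one.

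**3. Group-by-time test with the same f.** λ = f²N·m/(1 − ρ), df 4 and 4(N − 2), m = 5. N = 40, 28, 22 and 14 at ρ = 0, 0.3, 0.5 and 0.7. The figure 78 does not come from this formula.

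**4. What 0.80 would mean if the five-occasion between-groups test was the source.** That test compares arm means averaged over T0–T4, and randomised arms have no expected difference at T0.
- If d = 0.5 holds at T1–T4, the averaged effect is (0 + 4 × 0.5)/5 = 0.4. The variance factor at ρ = 0.5 is (1 + 4 × 0.5)/5 = 0.6. Then λ = (N/4) × 0.4²/0.6, which is 5.2 at N = 78 (power 61.5%) and 6.0 at N = 90 (67.8%). N = 120 gives 0.801.
- If f = 0.25 is already the five-occasion mean, 0.80 is right for that test, but the T1–T4 effect must be 0.5 × 5/4 = 0.625.

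**5. Illustration for contrasts that measure change from T0.** N = 90, d = 0.5 at T1–T4 and zero at T0, equal SDs, complete data, no baseline covariate (only BMI is named). For the two 1-df contrasts λ = (N/4)d²/v. For the omnibus test λ = (N/4)Σ(d_t − d̄)²/(1 − ρ), with Σ = 4 × 0.1² + 0.4² = 0.20.

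| Contrast | Variance term v | ρ = 0.3 | ρ = 0.5 | ρ = 0.7 |
|---|---|---|---|---|
| Change from T0 to one visit | 2(1 − ρ) | 50.9% | 65.0% | 85.7% |
| 4-df group-by-time | see formula | 49.5% | 65.7% | 88.7% |
| T1–T4 mean minus T0 | (1 + 3ρ)/4 + 1 − 2ρ | 70.8% | 84.3% | 96.9% |

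These are approximations to a GEE analysis. A simulation of 40,000 data sets (arms of 44 and 46, ρ = 0.5, robust-standard-error Wald tests) gave 67.0%, 69.8% and 85.5% in the same order. Null rejection was 5.5–5.7% for the 1-df tests and 7.0% for the 4-df test, so part of the difference is a liberal test.

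**The case against.** The strongest reply is that this is incomplete reporting and not an arithmetic error. Calling it a two-group comparison gives the number of arms and does not say there was a single measurement. The trial has five visits and a GEE, and a sensible repeated-measures setting returns exactly 78. This stands: a reader might infer from the 128 that 78 was miscalculated, and the document does not support that.

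It is also fair to say that the T0 argument rests on a reconstruction. A reader might take it as fact that the calculation averaged in the pre-treatment visit. It is not documented: four occasions at a correlation of about 0.46 also give 78, and those could be T1–T4 only. The T0 consequence must therefore stay conditional.

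A third reply is that f is normally the effect for the test being powered, in which case 0.80 is correct for that test. That is one of the two readings in step 4. It moves the question to whether d = 0.625 after baseline is what the sponsor meant by medium.

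Finally, the illustrative powers at 90 run from 49.5% to 96.9% and fall on both sides of 80%. They cannot support a claim that the trial is underpowered, and none is made. What the replies do not remove is that the stated 0.80 does not follow from the inputs given with it, and that the powered effect is not identified.

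**Conclusion.** The point holds as one of specification and interpretation. On its stated inputs the sentence should read 128, or about 59% power at 78; the shortfall is certain on those inputs because it needs no outside assumption. That 78 came from five occasions at correlation 0.5 is plausible but inferred. The lower power for a medium effect confined to T1–T4 (61.5% at 78, 67.8% at 90) is conditional on that source, on a constant d = 0.5 at T1–T4 and on ρ = 0.5. It is established, for the standard formula with the same f, that 78 is not a five-occasion group-by-time sample size, so the 0.80 should not be read as power for that effect.

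Two stronger conclusions should not be drawn: that 78 is a calculation error, and that the trial lacks power for every contrast of interest. At ρ = 0.5 the T1–T4 mean minus T0 has 84.3% power with 90 participants, and at ρ = 0.7 all three change contrasts in the table exceed 80%.

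**What to change.** Restate the sample-size sentence from the G*Power settings actually used: the test, the number of measurements, the correlation, and whether f refers to the T1–T4 effect or to the mean over all occasions. Attach 0.80 to that test only, and do not present it as power for the group-by-time effect in the GEE. If the settings were between-groups, five measurements and correlation 0.5, keep 78 and say that the power is for the group effect averaged over T0–T4.

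If power for the treatment-by-time effect is quoted, compute it from assumed values, not observed effects, label it as an illustration added to the original calculation, and show a correlation range with the favourable and unfavourable contrasts together. For example, at 90 participants with d = 0.5 at T1–T4 and correlation 0.5 (range 0.3 to 0.7): single-visit change 65.0% (50.9–85.7%), 4-df group-by-time 65.7% (49.5–88.7%), T1–T4 mean minus T0 84.3% (70.8–96.9%). Interpret any non-significant result from its confidence interval, not from the planned power.

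The cost is rewording one paragraph. No extra patients are needed. The downside is a less favourable power statement for some contrasts.

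### Minor: a target of 94 does not keep the stated minimum of 78 at 20% attrition; it does so only up to 17%, and 20% would need 98

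*Combined protocol and SAP*

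**What the plan says.** The combined protocol and SAP, under Sample Size Calculation and Randomization, reports a G*Power calculation with a medium effect (f = 0.25), alpha of 0.05 and "a statistical power of 0.80 for a two-group comparison". The result is: "The estimated minimum sample size was 78 participants". The next step is: "Allowing for an anticipated attrition rate of 20%, the target enrollment was increased to 94 participants". Allocation is 1:1, with 47 per group. The paragraph gives no formula for getting from 78 to 94. It also does not give the number of repeated measurements or the correlation that entered the power calculation.

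The Results section reports what happened: "four participants withdrew due to health-related reasons, resulting in a final sample size of 90". By arm, that is 46 controls and 44 participants assigned to light therapy.

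**The concern.** A reader takes an allowance for 20% attrition to mean that, if one in five enrolled participants is lost, the minimum number is still available. With 94 enrolled and a minimum of 78 that is not so. The paragraph therefore claims a protection that the target does not give, and nothing elsewhere in the document reconciles the three figures.

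What is at stake is the accuracy of the public sample size justification, not the validity of the trial. If the same step were copied into a later plan where losses came close to the anticipated rate, the study would end below its own minimum.

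**Working it through.** **Inputs.** Minimum 78, anticipated attrition 20%, target 94, f = 0.25, alpha 0.05 and power 0.80, all from Sample Size Calculation and Randomization. Two-sided testing, from Statistical Analysis. Four withdrawals and 90 remaining, from Results.

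**1. Where 94 probably comes from.** Adding 20% to the minimum gives 78 × (1 + 0.20) = 93.6, rounded up to 94, or 47 per group. This reproduces the plan's figure, but it is an inference because no formula is stated.

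**2. What 94 leaves at 20% attrition.** 94 × (1 − 0.20) = 75.2. Expected losses are 18.8; with 19 losses 75 remain, and 78 − 75 = 3 short. Rounding the losses down to 18 leaves 76, which is still below 78.

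**3. What 20% attrition requires.** N = 78 / (1 − 0.20) = 97.5, rounded up to 98 (49 per group). Check: 98 × 0.80 = 78.4, which is enough; 97 × 0.80 = 77.6, which is not. The target is 98 − 94 = 4 too low.

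**4. What 94 does tolerate.** 1 − 78/94 = 0.170, which is 16 losses. A 17th loss leaves 77.

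**5. What happened.** 4/94 = 4.3% attrition, and 90 − 78 = 12 above the minimum.

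**6. Cost in power of 75 instead of 78.** I used a noncentral F test of the group effect with 1 and N − 2 degrees of freedom and noncentrality λ = f² × N × m / (1 + (m − 1)ρ). Here m is the number of measurements and ρ their correlation. Both are assumptions, because the sample size paragraph gives neither.

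| Assumed setting | Smallest even N for 80% power | Power at 78 | Power at 75 | Loss (points, from unrounded values) |
|---|---|---|---|---|
| m = 5, ρ = 0.5 | 78 | 80.4% | 78.8% | 1.6 |
| m = 5, ρ = 0.3 | 58 | 90.8% | 89.6% | 1.1 |
| m = 5, ρ = 0.7 | 98 | 70.6% | 68.8% | 1.7 |
| single measurement | 128 | 58.7% | 57.0% | 1.7 |

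Of these rows, only the first agrees with the plan's 78 and 0.80. For it, λ = 0.0625 × 78 × 5/3 = 8.125 at N = 78, and 0.0625 × 75 × 5/3 = 7.8125 at N = 75. It is not the only setting that does so: three measurements with ρ = 0.4 (3/1.8 = 5/3) and two with ρ = 0.2 (2/1.2 = 5/3) have the same λ and also give 78. The other rows show only that the loss stays between 1 and 2 points whatever is assumed. They say nothing about the attrition step lowering power to those levels. Under the first setting, power at the reported 90 is 85.7%.

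**The case against.** There are four arguments on the other side.

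- **It is a matter of reading.** The sentence does not say in words that 78 will remain after a 20% loss, and 94 is exactly a 20% supplement to 78. This explains the number but does not make the claim true. Attrition is a share of those enrolled, and the Results count it that way (four withdrawals among 94 enrolled).
- **The number of completers may be the wrong unit.** The SAP analyses the outcomes by GEE and describes that method as able to handle missing data. A participant who leaves after some weekly assessments could still contribute, so 75 completers need not mean 75 analysed. This could soften the power cost. It does not reconcile 78, 20% and 94, and the Results themselves describe the final sample as those left after withdrawals.
- **Most of the power range does not apply.** Three of the four settings in the table cannot be the ones behind 78. That is fair: among settings consistent with the plan's own figures, the loss is 1.6 points. How 78 was obtained is a separate question and is not judged here.
- **Nothing turns on it now.** The document is dated 15 December 2024, three days after the stated study period ended, and 90 participants remained. This stands in full and sets the rating, but it does not make the sentence correct.

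**Conclusion.** The point holds as a minor reporting error. Taking the stated minimum of 78 as given and attrition as a share of those enrolled, 94 falls short by 3 completers at 20% attrition, or by 4 enrolled. Its true tolerance is 17.0%. These figures need no modelling assumption. The power cost of about 1 to 2 points, 1.6 under the settings examined that give 78, does rest on an assumed number of measurements and correlation.

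The shortfall did not occur, so it does not affect the enrolment, the analysis or the reading of the results.

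**What to change.** Keep 94 and the anticipated 20% as the historical planning figures and correct the sentence, for example:

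> We expected 20% of participants to be lost and planned to enrol 94. This number keeps at least 78 only if attrition does not exceed 17% (16 participants); 98 would have been needed to keep 78 at 20% attrition.

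If the authors can confirm that 94 was obtained by adding 20% to 78, they may say so, but the tolerance should be given either way.

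The cost is one sentence. No participants are added, and the target, the data and the analysis stay as they are. The stated tolerance becomes slightly less favourable, 17% instead of 20%.

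### The plan relies on unweighted GEE to cope with missing data but states neither the working correlation nor the dropout assumption; a mixed model on all 94 randomised would be valid under a wider condition, though the bias at the observed loss is small

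*Combined protocol and SAP*

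**What the plan says.** The Statistical Analysis section assigns all three outcomes (ISI-C, BFI-T and DT over T0 to T4) to GEE, described as methods "which account for correlated repeated measures and accommodate missing data". Under Primary and Secondary Outcomes the model is given "with BMI included as a covariate to adjust for baseline differences", and the text adds: "This model allowed for evaluation of group, time, and interaction effects on outcome measures". No working correlation, weighting, imputation, missing-data assumption or sensitivity analysis is stated.

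On losses, the Sample Size section says: "Allowing for an anticipated attrition rate of 20%, the target enrollment was increased to 94 participants". The Results section says that "four participants withdrew due to health-related reasons, resulting in a final sample size of 90", made up of "44 in the experimental group and 46 in the control group". It does not say when the four left, whether their earlier visits entered the models, or whether weekly questionnaires were missed by participants who stayed.

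**The concern.** Tolerating gaps in the data is not the same as being valid when they occur. Unweighted GEE generally needs dropout to be unrelated to outcome given the covariates in the model, and BMI is the only covariate named. The alternative is a correct working correlation, and none is stated. Withdrawal for health reasons is plausibly linked to insomnia, fatigue and distress, which are the outcomes. The loss was also uneven, at 3/47 against 1/47.

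If patients with worse scores leave one arm more often, the means of those who remain are no longer comparable, and the group-by-time estimate absorbs the difference. A likelihood-based mixed model with the same fixed effects remains valid when dropout depends on scores already recorded (missing at random, MAR), provided the incomplete records are in the data set.

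**Working it through.** **Inputs from the documents.** 47 per arm; five visits; f = 0.25, two-sided alpha 0.05, power 0.80, minimum N 78, attrition allowance 20%, target 94; losses of 3 and 1; ISI-C range 0 to 28.

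**The plan's own figures.** Take a repeated-measures F test between two groups with m = 5 visits and correlation 0.5 (the correlation is assumed; the documents give none). The noncentrality is f²·N·m/(1+(m−1)·0.5) = 0.0625 × 78 × 5 / 3 = 8.125 on 1 and 76 df, and power is 0.804. So 78 reproduces. The target is 78 × 1.20 = 93.6, rounded to 94. For two equal groups f = 0.25 corresponds to a difference of 2 × 0.25 = 0.5 SD.

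**Observed loss.** 4/94 = 4.3% overall; 3/47 = 6.4% light, 1/47 = 2.1% control. The standard error of a single-visit difference is √(2/47) = 0.206 SD.

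**Simulated bias, dropout depending on the previous score.** Assumptions: monotone dropout, logit P = a + b × previous score, b = 1.0 or 1.5 per SD, intercept set to give the stated loss in each arm, true effect 0, and either exchangeable correlation 0.5 or autoregressive correlation 0.7. Bias in the T0-to-T4 group contrast:

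| Loss, light / control | Independence GEE | Exchangeable GEE | Mixed model, unstructured |
|---|---|---|---|
| 3/47 v 1/47 | 0.02–0.03 SD towards light | within 0.01 SD | within 0.01 SD |
| 25/15% to 30/10% | about 0.04–0.13 SD towards light | up to 0.04 SD if the truth is autoregressive | within 0.02 SD |
| equal in both arms | about 0 | – | – |

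A second set used other assumptions: slope 2 per SD, true T4 effect −0.5 SD, autoregressive correlation 0.6 or exchangeable 0.5. At 6.4% v 2.1% it gave 0.024–0.033 SD towards light for independence GEE, 0.000–0.005 SD in size for exchangeable GEE and at most 0.003 SD for the mixed model. At 30% v 10%, independence GEE reached 0.111–0.151 SD, the upper end reflecting the steeper slope.

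**Relative size.** At the observed loss: 0.02/0.20 = 10% to 0.03/0.20 = 15% of a standard error, about one-eighth. At the planned loss with an uneven split: 0.04/0.5 = 8% to 0.13/0.5 = 26% of the design effect.

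**Dropout depending on the unseen current score (missing not at random, MNAR).** Large-sample runs of the second set, independence GEE against mixed model:
- 6.4% v 2.1%: 0.041–0.047 SD falls to 0.024–0.031 SD.
- 30% v 10%: 0.18–0.21 SD falls to 0.12–0.135 SD.

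The share removed is 25–48%. A noisier run at trial size with stronger within-person correlation gave about two thirds (0.042 to 0.014 SD), so the share depends on assumptions that the documents cannot settle.

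**If only the 90 are analysed.** On one simulated set of 44 v 46 with all five visits complete and BMI in the model, independence GEE, exchangeable GEE and a random-intercept mixed model gave identical group-by-time estimates. Changing the model then removes none of the bias.

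**Bound without a dropout model.** If the four missing T4 values could lie anywhere on the ISI-C, the group difference in means can range over at most 28 × (3/47 + 1/47) = 2.4 points.

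**The case against.** The strongest reply is about size. Four of 94 were lost, and the bias is about one-eighth of a standard error even for the least favourable working correlation. Naming a sensible working correlation would do nearly all the work at that loss. The larger figures need a 20% loss with an uneven split; the plan allows for 20% overall, gives no split, and reports 4.3%. It can also be said that the quoted sentence is literally true, since GEE does not require complete cases. All of this stands and limits the point to an improvement. It does not supply the missing working correlation or dropout assumption, and missed questionnaires are unreported, so total missingness may exceed four participants.

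Three stronger readings are tempting, and the documents do not support them:
- *A mixed model on the same data removes most of the bias.* This holds under MAR with all available visits. It fails if the data set is 90 completers, and holds only in part if dropout followed unseen health.
- *The bias favours light.* This describes independence GEE with greater outcome-related loss from the light arm. Exchangeable GEE under autoregressive data, and a completers' analysis of change, can be biased slightly against light.
- *Sicker patients left the light arm more often.* A split of 3 v 1 is compatible with chance (Fisher two-sided p about 0.62), and nothing says that the four had worse scores.

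**Conclusion.** The point holds as a gap in justification with a cheap remedy. The plan credits GEE with handling missing data without stating the condition under which it does so, and its own account of health-related, uneven withdrawals makes that condition doubtful. The wording about the final sample suggests, without saying outright, that the withdrawn participants were excluded.

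At the reported loss the consequence is small and unlikely to change the conclusion. It would have mattered more at the planned attrition with an uneven split. These sizes rest on assumed correlations, dropout slopes and true effects, none of which the documents give. A reader should not infer that the GEE results are wrong.

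**What to change.** 1. Analyse all 94 as randomised, using every available visit, in a likelihood-based repeated-measures mixed model with group, time, group × time and BMI, and unstructured covariance across T0 to T4. State that it is valid under MAR.
2. Keep GEE as a sensitivity analysis and name its working correlation.
3. Qualify the sentence on missing data: unweighted GEE uses incomplete records, but is generally valid only if dropout is unrelated to outcome given the covariates or the working correlation is correct.
4. Add one MNAR check, delta-adjusted or tipping-point, because health-related dropout may depend on scores never recorded.
5. Report the timing and reason of each withdrawal by arm, how the four were handled, and the number of questionnaires received at each visit.

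The cost is about one paragraph and a different model procedure. The Abstract puts the analysis in the future tense, while the Statistical Analysis section reports it as done. If outcome data have been seen, the change must be declared as post hoc.
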